3.2.6.4. SAMPLE SIZE ANALYSIS

The current study is designed to demonstrate non-inferiority using a non-inferiority margin equal to -10.0% at a 1-sided type 1 error rate of $\alpha=0.05$. Subclassification using propensity score (PS) quintiles will be used to minimize selection bias arising from the non-randomized device group comparison. Mantel-Haenszel stratified analyses accounting for PS subclass will utilized when testing the primary non-inferiority hypothesis. A total of 182 two-level investigational subjects will be enrolled and compared to two level ACDF control subjects. The pool of two level ACDF control subjects includes a sample size of N=188. The sample size analyses below demonstrate that these sample sizes are sufficient to test the primary non-inferiority hypothesis after accounting for loss-to-following and PS ‘trimming’ of controls during the observational design phase.

According to Table 28 contained in the [REDACTED] SSED, the overall success was achieved in [REDACTED] controls. Therefore, the control group Month 24 CCS probability was assumed to be 70%. The total control sample size reported in the SSED is N=188. Since selection into a PS sub class will be conducted without access to outcome data, it is assumed that 85% of the selected controls will have a complete Month 24 CCS endpoint. It is also assumed that up to 20% of the controls will be trimmed as part of the PS modeling process. Therefore, for purpose on initial sample size analysis, the control sample size is assumed to be $N = 188 * .85 * .80 = 128$.

It is noted that the 2-level [REDACTED] group experienced an [REDACTED] success rate. For the purpose of sample size analysis, it is assumed that the 2-level Simplify disc

group will have at least a small true superiority margin of 3.5%. That is, it was assumed that the true probability of Month 24 CCS for the investigational group is 75.0%. As noted above, the primary effectiveness hypothesis is non-inferiority with a non-inferiority margin of -0.10 to be tested using at one-sided $\alpha=0.05$. With these assumptions, 154 investigational device patients are required for 80% statistical power as determined using industry standard software (nQuery Advisor 7.0 module PTE0U-1).

“When the sample sizes in the groups are 128 and 154, a two-group large-sample normal approximation test of proportions with a one-sided 0.050 significance level will have 80% power to reject the null hypothesis that the test and the standard are not equivalent (the difference in proportions, $p_T - p_s$, is -0.100 or farther from zero in the same direction) in favor of the alternative hypothesis that the proportions in the two groups are equivalent, assuming that the expected difference in proportions is 0.035 and the proportion in the standard group is 0.700.”

To account for up to 15% loss-to-follow-up, the total enrolled investigational sample size will be N=182.

3.2.6.5. ANALYSIS SETS

The study contains two treatment arms with patients receiving either two-level Simplify Disc or two-level ACDF. The following subject groups or analysis sets will be used to complete the analysis of data.

- Intent-to-treat (ITT) analysis set: The ITT analysis set will include all enrolled patients in which treatment was attempted as defined by the recording of incision time and excluding training cases. Patients will be included according to their intended treatment device. Since the investigational and control treatments are to be performed at different institutions, it is not possible for subjects to receive the alternative treatment. Therefore, the ITT analysis set will be used in safety analyses.

- Primary Effectiveness (PE) analysis set: The PE analysis set includes all subjects in the ITT analysis set that are selected into a propensity score subclass. Primary effectiveness analyses will be conducted using the PE analysis set. Selection into a PS subclass is the observational study equivalent to being randomized. Intraoperative failures will be included in primary non-inferiority testing as composite clinical endpoint failures. Patients with no follow-up subsequent to surgery will be treated as having a missing primary composite clinical endpoint and will be handled according to the approaches outlined below.
- Per protocol (PP) analysis set: The PP analysis set will include patients in the PE analysis set that have no major protocol deviations including clinically significant deviations from inclusion or exclusion criteria. Secondary efficacy analyses will be performed using the PP analysis set.
- Training cases analysis set: Training case safety and effectiveness data will be summarized separately.
- Original Protocol (OP) analysis set: All patients enrolled in the original protocol prior to approval of the subject protocol with the [REDACTED] historical control will be analyzed separately to determine if they would meet the current patient enrollment criteria. OP safety and effectiveness will be summarized separately and compared to the ITT analysis set. Please note, due to the small sample size, these comparisons will lack statistical strength and will be provided for informational purposes only.

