3.2.6.14. OTHER OUTCOMES

Other outcomes to be measured include:

- Duration of hospitalization;
- Blood loss;
- Operative time (skin incision to skin closure);
- In vivo endplate thickness analysis will be completed on a consecutive series of the first 25 subject who complete the 24 month follow up visit.

Radiographs will be used to monitor the occurrence of some of the above adverse events, including subsidence of the device into the adjacent disc or other changes in the implant, and spinal instability. In addition, at each visit, after the subject has had an opportunity to spontaneously mention any problems, the investigator will elicit information concerning adverse events by asking standard questions. Adverse events considered unusual for the patient population (i.e., occurring with greater frequency than anticipated or with greater severity than anticipated), key to safety or efficacy, or device related will require detailed reporting on the appropriate case report form.

Subgroup Analyses

Primary and secondary effectiveness endpoints will be evaluated in subgroups defined by stratifying the primary effectiveness analysis set. Safety endpoints will be evaluated in subgroups defined by stratifying the safety analysis set. Subgroups to be evaluated will include, but not limited to:

Gender (Male vs. Female)

Age (Median cut point, ≥ 55 and < 65 years)

Height (Median cut-point)

Weight (Median cut-point)

BMI (Median cut-point)

Comorbidities

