3.2.7.6. CLINICAL EVENTS COMMITTEE

The Clinical Events Committee (CEC) will adjudicate all reported adverse events. This will include all SAEs, including secondary surgeries at the index and adjacent levels, primary endpoint failure, and neurologic deterioration.

The CEC may determine neurologic status has declined at 24 months compared to baseline based on changes including:

- Motor Assessment: shift from baseline.
- Sensory Examination: shift from normal to absent or impaired; impaired to absent.
- Myelopathic Gait Abnormality Class: any worsening.

The CEC will also review all UADEs. Adverse events will be classified by the CEC based on seriousness, relationship to device and procedure, and severity. The CEC will also adjudicate protocol deviations. The CEC will consist of three spine surgeons who are not affiliated with the Sponsor or who are not participating in the study. The recommendations of the CEC and become part of the clinical trial data set.

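### The plan assigns secondary efficacy analyses to the per-protocol set but subgroup analyses of the secondary endpoints to the primary effectiveness set, and no readable section says which set carries the overall secondary result

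*Combined protocol and SAP*

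**What the plan says.** All references are to the combined protocol and SAP.

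Section 3.2.6.5 (Analysis Sets) builds three nested sets:

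- ITT: "all enrolled patients in which treatment was attempted as defined by the recording of incision time and excluding training cases".
- PE: "The PE analysis set includes all subjects in the ITT analysis set that are selected into a propensity score subclass". The section adds: "Selection into a PS subclass is the observational study equivalent to being randomized". It then gives PE its job: "Primary effectiveness analyses will be conducted using the PE analysis set".
- PP: "The PP analysis set will include patients in the PE analysis set that have no major protocol deviations". Clinically significant eligibility deviations are the only kind it names. It then says: "Secondary efficacy analyses will be performed using the PP analysis set".

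Section 3.2.6.14 (Other Outcomes, Subgroup Analyses) uses a different set for the same endpoints: "Primary and secondary effectiveness endpoints will be evaluated in subgroups defined by stratifying the primary effectiveness analysis set".

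Section 3.2.6.13, which lists the secondary endpoints, names no analysis set. Sections 3.2.6.11 and 3.2.6.12 are redacted.

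On deviations, section 3.2.7.6 says: "The CEC will also adjudicate protocol deviations". The same committee (CEC) adjudicates adverse events, primary endpoint failure and neurologic deterioration.

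**The concern.** There are two problems.

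The first is consistency. If the overall secondary result is in PP and the subgroup results are in PE, the subgroup counts will not add up to the overall count once anyone is excluded from PP. A reader of the report could not tell whether a difference between the two reflects the subgroup or the change of set.

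The second is bias. In this non-randomized comparison, protection against selection bias comes from forming the PS subclasses without outcome data and verifying balance on that sample (section 3.2.6.3). PP removes patients afterwards, and every one of them has been treated. The readable text does not say that deviations are judged blind to outcome, that deviations in the historical controls will be classified to the same standard, or that balance will be checked again. The endpoints exposed are those compared between groups, such as neck and arm pain, motor and sensory status, time to recovery, SF-36, satisfaction and return to work.

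**Working it through.** **Which set for which analysis.** Setting the sections side by side:

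| Analysis | Set | Section |
|---|---|---|
| Primary effectiveness | PE | 3.2.6.5 |
| Superiority | PE | 3.2.6.7 |
| Secondary efficacy analyses | PP | 3.2.6.5 |
| Secondary endpoints, by subgroup | PE | 3.2.6.14 |
| Secondary endpoints, list and definitions | none named | 3.2.6.13 |

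Taken literally, the third and fourth rows put the same endpoints on different sets.

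**Who is removed.** PP lies within PE and PE within ITT, and entry to ITT requires a recorded incision. Every patient in PE but not in PP has therefore been treated.

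**Headcount illustration.** The plan gives no expected rate of major deviations. Assume all 182 device patients are in PE and 10% have a major deviation: 0.10 x 182 = 18.2, about 18 patients. The male and female subgroups would then total 182, against an overall secondary count of 182 - 18 = 164.

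**Size of a possible shift.** The plan has no figure of its own to reproduce here. Let x be the share of one arm excluded, R the success rate among those retained and E the rate among those excluded. The full-arm rate is (1 - x)R + xE, so moving from PE to PP changes that arm's rate by

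R - [(1 - x)R + xE] = x(R - E).

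With assumed values of x and of the gap R - E, and no exclusions in the other arm:

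| x | gap -30 | gap -10 | gap 0 | gap +10 | gap +30 |
|---|---|---|---|---|---|
| 5% | -1.5 | -0.5 | 0 | +0.5 | +1.5 |
| 10% | -3.0 | -1.0 | 0 | +1.0 | +3.0 |

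Entries are percentage points. As a check with a wider gap, take a full-arm rate of 70%, x = 10% and E = 35%. The retained rate is (0.70 - 0.10 x 0.35)/0.90 = 0.739, a shift of 3.9 points. The formula agrees: 0.10 x (73.9 - 35) = 3.9.

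If both arms lose patients, the change in the between-group difference is the device shift minus the control shift. Similar exclusions in both arms largely cancel.

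**The case against.** The strongest defence is that the PP sentence means supportive analyses of efficacy, not analyses of the secondary endpoints. It sits inside the PP definition, and where the plan clearly means the endpoints it calls them effectiveness endpoints and, in 3.2.6.14, ties them to PE. On that reading the clash disappears. The terminology does not settle it, because the protocol uses efficacy and effectiveness loosely elsewhere (for example in 3.2.5.4.5). Even if the reading is accepted, no readable section then names a set for the overall secondary analysis. A clarification is needed either way, although the redacted sections might supply it.

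It is also fair that using one set overall and another for subgroups is not logically impossible. No readable section attaches an alpha level or success criterion to the secondary endpoints. Several of them (left and right arm pain, adjacent-level deterioration, migration, the dysphagia index, facet deterioration) are for the investigational group only and have no between-group comparison to bias. All of this stands and limits the consequences.

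A reader might go further than the documents allow in four ways:

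- That the CEC judges deviations knowing outcomes. Section 3.2.7.6 gives it both tasks but no timing, and says nothing on what it knows when it classifies a deviation.
- That control deviations were defined under different rules. The control trial's description in 3.2.4.2 is heavily redacted and does not discuss deviations. What is missing is a stated common standard.
- That excluded patients do worse, so PP flatters the device. The only named deviations concern eligibility, and nothing shows how such patients fare or which arm would lose more.
- That exclusions destroy balance within subclasses. The subclass labels and the stratified analysis remain available in PP. Balance may be disturbed, and the plan does not provide for checking it.

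**Conclusion.** The point holds as an assignment to reconcile, with a possible bias of unknown direction in the comparative secondary endpoints if section 3.2.6.5 is followed literally. Excluding 10% of one arm only, with a gap of -30 to +30 points, gives about -3 to +3 points; at 5% it is about -1.5 to +1.5; with no gap it is zero. The exclusion rate, the gap and the one-arm pattern are assumptions, since the documents give none of them. One-sided exclusion is the unfavourable case.

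A reader might infer that the main conclusion of the trial is at risk. It is not: the primary non-inferiority test and the superiority test are both on PE. The change is still worth making, because it keeps the secondary comparisons on the sample whose balance was established without outcome data.

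**What to change.** Replace the PP sentence in section 3.2.6.5 with text to this effect, and refer to it from 3.2.6.13:

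*Secondary effectiveness endpoints will be analysed in the PE set. Between-group comparisons will be stratified by PS subclass; endpoints collected only in the investigational group will be summarised in the PE device patients. The primary and secondary endpoints will be repeated in the PP set as supportive analyses.*

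This agrees with 3.2.6.14 and drops no planned analysis. If the redacted sections already assign the set, a cross-reference is enough, provided the PP sentence is brought into line.

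The cost is a short text change, since both sets are already defined and no new data are needed. The downside for the sponsor is that secondary results may be slightly less favourable than in PP, if the excluded device patients turn out to have done worse.

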3.2.6.6. NON-INFERIORITY TESTING

The primary non-inferiority test will be conducted using a Mantel-Haenszel stratified analysis approach to pool over PS subclass specific estimated device group differences. If the one-sided p-value for non-inferiority is less than or equal to 0.05, it will be concluded that the two-level Simplify Disc is non-inferior to the two-level ACDF control. In addition to hypothesis testing, the lower bound of a one-sided 95% confidence for the true difference of the device group difference will be determined.

3.2.6.7. SUPERIORITY TESTING

If the non-inferiority study success criterion is met, superiority testing will be performed in the PE analysis set. It will be concluded that the two-level Simplify Disc is superior to the two-level ACDF control if the one-sided p-value for superiority is less than or equal to 0.025. By the closed testing principal there is no need for a multiplicity adjustment when testing superiority after rejecting the inferiority null hypothesis. Note that 1-sided $\alpha=0.025$ is specified for testing of superiority rather than 0.05 in order to have more definitive evidence to support the stronger claim of superiority.

3.2.6.8. HANDLING OF MISSING DATA FOR PRIMARY CCS ENDPOINT

The first approach to be used to handle missing data for the primary CCS endpoint is to limit the expected amount of missing data through exceptional study conduct and management and this is the goal of all study personnel. However, some missing data from lost to follow-up is inevitable in these types of clinical trials. Moreover, it is known that some control patients were not evaluable for the primary Month 24 CCS endpoint.

The following two approaches will be used in testing of the clinical non-inferiority hypotheses stated above.

- 1) Complete case analysis followed by tipping point sensitivity analysis (see below); and
- 2) Multiple imputation (MI) (see below).

The primary non-inferiority test will be conducted using the multiple imputation approach described below. The complete case analysis followed by tipping point analysis will be performed as a sensitivity analysis for the assumptions inherent in MI.

Multiple imputation (MI)²⁹ is a methodology used to address missing values due to LTF and possibly other reasons. The validity of MI depends on an untestable assumption known as

²⁹ Rubin DB and Schenker N. Multiple imputation in health-care databases: An overview and some applications. *Statistics in Medicine* 1991 10:585-598.

missing at random (MAR)³⁰ which is a much weaker assumption than missing completely at random (MCAR) which requires unconditional independence. Although MAR is likely to hold in many more situations than MCAR, in any given situation there is no way to confirm whether the assumption of MAR is tenable and consequently, whether or not the MI analysis produces valid inference. For this reason, a complete case analysis followed by a tipping point sensitivity analysis will be conducted in sensitivity analyses (see below). MI will be used to impute missing final NDI in patients otherwise evaluable for primary CCS. For each imputation, the composite endpoints would be constructed from the imputed NDI values and within randomly completed data sets, the device group difference and standard error is determined. For these imputations, the status of the other CCS components will be based on available data up to the point of loss-to-follow-up which is essentially a last-observation-carried forward approach. In this case, the patient's Month 24 secondary surgical intervention status, major device-related complication status, and neurological success status will be inferred from their Month 12 status. Imputations for NDI will be repeated 20 times to produce 20 randomly completed data sets. The final device group difference will be the average of the multiple imputed datasets and its standard error will account for both within (usual) and between imputation error as described in Rubin and Schenker 1991. The MI standard error will be used in the derivation of the p-value to test the non-inferiority hypothesis. MI analyses will be performed using SAS³¹ Proc MI and MIANALYZE or their equivalent.

A complete case analysis followed by a tipping point analysis will be conducted to complement the primary MI approach in order to evaluate the robustness of statistical conclusions to the assumptions inherent in MI analyses. This includes the untestable assumption; namely, that the probability that a value is missing is independent from the value itself conditional on baseline values and clinical status up to the point. In a tipping point analysis, missing values in each group are separately assumed to be either successes or

³⁰ Rubin DB Inference and missing data. Biometrika 1976, 63:581-592.

³¹ SAS Institute, Cary NC.

failures. Treatment group differences will be computed based on all possible combinations of assigning success or failure to the primary overall success endpoint to the patients in the two groups. For example, one scenario will be that all missing two-level Simplify values are failures and all missing two-level ACDF values are successes. The next scenario would have one success and the remaining missing values as failure for two-level Simplify keeping all missing two-level ACDF as successes, and so forth. The 1-sided p-value for testing the primary non-inferiority hypotheses will be determined for each scenario. These results will be plotted using a dot plot with the number of missings assumed as failures for two-level Simplify on the x-axis and the number of missing assumed as failures for two-level ACDF on the Y-axis. The dots will be color coded to indicate whether or not the primary statistical conclusion changes under each individual scenario. If the fraction of scenarios in which the statistical conclusion changes is small, the primary results will have been shown to be robust against assumptions concerning missingness.

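### The tipping-point robustness rule counts how many cells flip, not how far from missing at random the flips lie

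*Combined protocol and SAP*

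**What the plan says.** Section 3.2.6.8 makes multiple imputation the primary method. It concedes that the missing-at-random (MAR) assumption cannot be verified, and it gives a complete-case analysis followed by a tipping-point analysis the job of testing it.

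The grid is exhaustive: "Treatment group differences will be computed based on all possible combinations of assigning success or failure to the primary overall success endpoint". For each cell, "The 1-sided p-value for testing the primary non-inferiority hypotheses will be determined for each scenario". A dot plot then puts the assumed number of failures per arm on the two axes, with colour showing whether the conclusion changes. The reading rule is: "If the fraction of scenarios in which the statistical conclusion changes is small, the primary results will have been shown to be robust".

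The section gives no value for small and no weighting of cells. It does not mention the cell implied by MAR or by the observed success rates.

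The test applied in each cell comes from elsewhere. Section 3.2.6.4 says the study is "designed to demonstrate non-inferiority using a non-inferiority margin equal to -10.0"%, and Section 3.2.6.6 sets the level: "If the one-sided p-value for non-inferiority is less than or equal to 0.05", non-inferiority is concluded. Section 3.2.6.6 also makes the test a Mantel-Haenszel analysis stratified by propensity-score (PS) subclass.

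**The concern.** A tipping-point analysis should show how far the missing patients' outcomes must depart from what MAR implies before the conclusion is lost, and whether a departure of that size is believable. The fraction of flipped cells answers a different question. The corner where every missing Simplify patient fails and every missing ACDF patient succeeds counts as much as a cell next to the observed rates. The fraction therefore moves with the number missing in each arm and with where the MAR cell sits in the grid.

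This is the only stated standard for calling the primary result robust to data missing not at random, and the comparison is non-randomized with up to 15% missing planned in each arm. Without a cutoff, robustness can be claimed or denied after the fraction is known. With one, a result that survives large departures could be marked fragile and one that tips easily could be marked robust.

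**Working it through.** **Inputs from Section 3.2.6.4.** Margin −0.10, one-sided 0.05, 182 Simplify patients enrolled. Selected controls: 188 × 0.80 = 150.4, so 150. With 85% evaluable: 182 × 0.85 = 154.7, so 155 observed and 27 missing; 150 × 0.85 = 127.5, so 128 observed and 22 missing. Control rate: "the control group Month 24 CCS probability was assumed to be 70"%. The power statement says "the expected difference in proportions is 0.035 and the proportion in the standard group is 0.700", which gives Simplify 0.735. The same section also says "the true probability of Month 24 CCS for the investigational group is 75.0"%; that conflicts, but nothing below depends on it.

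**The plan's own figure.** SE = √(0.735 × 0.265/154 + 0.70 × 0.30/128) = 0.0539. Power = Φ((0.035 + 0.10)/0.0539 − 1.645) = Φ(0.86) = 80.5%, against 80% stated. With 0.75 in place of 0.735 it is 87.7%, so the stated 154 rests on 0.735.

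**Test per cell.** With i assumed Simplify failures and j assumed ACDF failures among the missing, complete the two arms and compute z = (p_T − p_C + 0.10)/√(p_T(1−p_T)/n_T + p_C(1−p_C)/n_C). The cell flips if z < 1.645. PS strata are ignored.

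**Two results, assumed counts, both totalling 182 and 150**

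| | Result A | Result B |
|---|---|---|
| Simplify observed; missing | 114/155 (73.5%); 27 | 125/178 (70.2%); 4 |
| ACDF observed; missing | 102/146 (69.9%); 4 | 90/128 (70.3%); 22 |
| Complete-case p | 0.004 | 0.031 |
| Grid | 28 × 5 = 140 | 5 × 23 = 115 |
| Cells that flip | 50 (35.7%) | 25 (21.7%) |
| Flip probability, missing outcomes at observed rates | 0.01% | 10.8% |
| Same, missing Simplify 10 points worse | 0.5% | 14.9% |
| Same, 20 points worse | 6.4% | 19.6% |
| Patients to change from MAR cell to nearest flip | 10 | 4 |
| Joint adverse shift at which non-inferiority is lost | about 31 points | about 10 points |

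*Cell counts.* In A, with j = 0, 1, 2, 3, 4 ACDF failures, flips start at 16, 17, 18, 19, 20 Simplify failures out of 27: 12 + 11 + 10 + 9 + 8 = 50. In B, with j = 0 to 6, they start at 0, 0, 0, 1, 2, 3, 4 out of 4: 5 + 5 + 5 + 4 + 3 + 2 + 1 = 25.

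*Joint shift.* Lower the missing Simplify success rate and raise the missing ACDF rate by the same amount s from the observed rates.
- A at s = 0.308: Simplify 0.735 − 0.308 = 0.427; ACDF reaches its cap of 1.00. Completed rates: (114 + 27 × 0.427)/182 = 0.690 and 106/150 = 0.707. z = (−0.017 + 0.10)/0.0506 ≈ 1.64.
- B at s = 0.100: Simplify 0.602, ACDF 0.803. Completed rates: (125 + 4 × 0.602)/182 = 0.700 and (90 + 22 × 0.803)/150 = 0.718. z = (−0.018 + 0.10)/0.0500 ≈ 1.64.

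The rule scores A worse than B; every measure of distance or plausibility in the table scores A better. A pooled-variance test gives the same 35.7% and 21.7%.

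**Planning pattern.** With 114/155 and 27 missing against 90/128 and 22 missing (p = 0.007), 167 of 644 cells flip (25.9%). Every flipped cell needs the missing Simplify failure rate to exceed the missing ACDF failure rate by at least 27 points. The flip probability at observed rates is 0.3%.

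**Where the rule behaves.** Hold 27 and 22 missing and ACDF at 90/128. As Simplify rises through 108, 111, 114, 117 and 120 of 155, the fraction falls: 44.3%, 34.5%, 25.9%, 18.5%, 12.4%. That is the right order. If the ACDF rate also varies, reversals appear but stay under 3 percentage points of cells.

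**The case against.** **The plan ranks nothing.** The rule meets one dataset with one missingness pattern, and with the missing counts and ACDF rate fixed it orders results sensibly. A reader might infer from A and B that the fraction generally misorders results; the calculations do not support that. A clear reversal needs different missing counts, and both examples depart from the plan's assumptions: A has 4 of 150 controls missing where 15% is assumed, and B has 4 of 182 Simplify patients missing where up to 15% is allowed. This stands as a limit on the claim. It does not rescue the rule, because the missing counts are unknown in advance and the cutoff is unspecified: any value between 21.7% and 35.7% passes B and fails A.

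**The yardstick matters.** Not every pair with different missingness is a reversal. Take 113/154 (28 missing) against 90/128 (22 missing), and 123/176 (6 missing) against 98/140 (10 missing). The fractions are 27.7% and 19.5%, and flip probabilities at observed rates are 0.5% and 6.7%, which looks like a reversal. Yet both tip at a joint shift of about 16 points, and at a 20-point joint shift the first flips more often (74% against 64%). More missing data does mean more exposure. Hence the reliance here on A and B, whose order holds on every measure tabulated.

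**Location is already displayed.** The dot plot shows the boundary. True, but the written criterion uses only the share of cells, and nothing marks the MAR point.

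**Low consequence.** A reader might infer that study success is at risk. It is not: Sections 3.2.6.2, 3.2.6.6 and 3.2.6.8 rest success on the primary multiple-imputation test, and the tipping-point analysis is supportive.

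**Conclusion.** The point holds in a limited form. The stated criterion does not measure how large a departure from MAR overturns non-inferiority, and it can point the wrong way: 35.7% of cells for a result that tips at about 31 points, 21.7% for one that tips at about 10. The defect affects what may be called robust, not whether the trial succeeds.

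The sizes rest on assumed observed counts at the planned totals and on an unstratified Wald test. The planned stratified test could shift individual cells, and Section 3.2.6.8 does not say how assumed outcomes are spread over PS subclasses. Sections 3.2.6.11 and 3.2.6.12 are redacted and could not be checked for further rules. The documents do not support the stronger readings that the fraction is always misleading, or that it would misjudge this trial if missingness follows the plan.

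**What to change.** Replace the fraction sentence in Section 3.2.6.8 with a location-based criterion:

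- Report the success rates among missing patients in each arm, and the joint shift from the observed or imputation-implied rates, at which non-inferiority is lost.
- Mark the MAR point on the dot plot.
- Call the result robust if the boundary lies outside a departure range that the sponsor justifies and fixes before outcome data are seen. The end of the PS design stage, before unblinding (Section 3.2.6.3), is a natural time. No particular width is implied: a 20-point no-flip rule, for instance, would fail the 113/154 against 90/128 case above at its adverse corner.
- State how assumed outcomes are allocated to PS subclasses, so that each cell uses the stratified test, for example by averaging over random allocations.

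The cost is about a paragraph of text, some extra computation (a stratified cell has no single p-value until allocation is defined), and a commitment in advance to a plausibility range. The primary test, sample size and success criterion stay as they are.
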